Main Research Variable(s): The independent variables are (1) the 12-week program of TEHE alone, (2) the 12-week program of acupressure only, (3) the 12-week program of combined acupressure and TEHE (TEHE Plus), (4) the 12-week program of combined MBI and TEHE and (5) control (usual care). Outcome variables are fatigue, physical activity, contributing factors of fatigue (depressive symptom, anxiety, sleep, relationship with others), and biomarkers.

Design: Repeated measures randomized controlled trial design.

Setting: Participants will be recruited through the Comprehensive Cancer Center, Johns Hopkins University.

Sample: A total of 105 participants will be recruited from 2 populations

Population 1: Individuals diagnosed with solid tumor cancer; who had completed all primary cancer treatment (surgery, chemotherapy, and radiation therapy) within at least 3

Date: September 26, 2024

Principal Investigator: [name]

Application Number: IRB00154198

months OR prostate cancer completed all primary cancer treatment and have hormone therapy for at least 6 month, aged 21 years or older, experiencing fatigue in the past 7 days on average of $\geq 3/10$, self-report ability to complete the 6 min walk test with a perceived exertion of 6 or below on a scale 1 (hardly any exertion) to 10 (feels almost impossible to keep going), can communicate in English and own a smart phone.

Population 2: individuals diagnosed with solid tumor cancer; who are receiving immunotherapy for at least 3 months before enrollment, aged 21 years or older, experiencing fatigue in the past 7 days on average of $\geq 3/10$, self-report ability to complete the 6 min walk test with a perceived exertion of 6 or below on a scale 1 (hardly any exertion) to 10 (feels almost impossible to keep going), can communicate in English and own a smart phone.

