The mean and standard deviation of each outcome measure, recruitment rate, drop out, acceptability, tolerability will be calculated per group per study visit. The study primary aim the feasibility of a 12-week technology-enhanced home exercise (TEHE) program and TEHE plus program (***Aim 1***) will be analyzed using descriptive statistics of eligible participants and recruited participants, a number of participants completing the intervention program, compliance (number of participants complete the daily step goal), and participants' satisfaction and opinion of the intervention. To examine the effect of the TEHE program on fatigue, physical activity and serum biomarkers (Heat Shock Protein 90 and Brain-Derived Neurotrophic Factor) (***Aim 2***), the paired t-test will be used to analyze the effect of the program on fatigue, PA and biomarkers at the end of the program compared to baseline. The student t-test will be used to compare the variables among participants in the TEHE program, Acupressure only, TEHEplus, and TEHE +MBI compare to the usual care (control) group.

The secondary aims: The change of fatigue and physical activity level in week 12 compared to baseline will be calculated. Analysis of Variance (ANOVA) will be used to compare the effect of the TEHEplus, combined TEHE, and MBI with the TEHE only and Acupressure only on fatigue and physical activity (***Aim 3***). Change from baseline to 12 weeks will be computed for serum HSP90AA1 and BDNF levels. ANOVA will be used to examine the differences of change in serum biomarkers at week 12 compared to baseline in the TEHE only, Acupressure only, TEHEplus, TEHE +MBI and control (usual care) groups (***Aim 4***).

Sample size justification

Sufficient information from prior studies is not available for us to conduct a sample size calculation for the proposed multilevel analyses. The purpose of this pilot project is to explore the feasibility of the program and the relationships between the trajectories of the outcome measures, and not to achieve high power. The proposed N of 110 (22 participants/group) will likely result in low (below 0.60) statistical power. Results obtained will inform future power analyses for full-scale studies.

Early stopping criterion for safety/futility/efficacy as needed.

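### The planned total is 105 in the abstract but 110 (22 per group) in the statistics section, and the sample size justification refers to multilevel analyses that the analysis plan does not contain

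*Combined protocol and SAP*

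**What the plan says.** Section 1 (Abstract), Sample, gives the recruitment target: "A total of 105 participants will be recruited from 2 populations". The list of independent variables in the same section numbers five groups and ends with "4) the 12-week program of combined MBI and TEHE and (5) control (usual care". The randomization paragraph of Section 4 and the eligibility text of Section 5 also name four interventions and a control group.

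Section 7, Sample size justification, gives a different target: "The proposed N of 110 (22 participants/group) will likely result in low (below 0.60) statistical power". It explains why there is no formal calculation: "Sufficient information from prior studies is not available for us to conduct a sample size calculation for the proposed multilevel analyses". It describes the aim of the pilot as exploring feasibility and "the relationships between the trajectories of the outcome measures, and not to achieve high power".

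Section 7, Analysis plan, comes immediately before that justification and sets out these analyses:

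- **Aim 1 (feasibility):** descriptive statistics.
- **Aim 2:** paired t-tests of week 12 against baseline and, between groups, "The student t-test will be used to compare the variables among participants in the TEHE program" and in the other intervention arms, each against usual care.
- **Aim 3:** "The change of fatigue and physical activity level in week 12 compared to baseline will be calculated", followed by ANOVA across the four intervention arms.
- **Aim 4:** "ANOVA will be used to examine the differences of change in serum biomarkers at week 12 compared to baseline" across all five groups.

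**The concern.** Two current statements of the planned size disagree, so at least one is wrong as written. The target matters even in a pilot. Recruitment and retention are part of the feasibility aim, and a trial that closes at 105 meets the abstract's target while falling 5 short of the one in the statistics section.

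The second problem lies in the justification itself. It excuses the lack of a calculation by pointing to multilevel analyses that it calls proposed, yet the plan proposes none. It also states a purpose, relating the courses of the outcomes to one another, that no listed analysis serves. A reader cannot tell which analysis the sample size was considered for.

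**Working it through.** **1. The two totals**

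Inputs: 105 (Section 1, Sample); 110 and 22 per group (Section 7, Sample size justification); five groups (Sections 1, 4 and 5).

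- Plan's own figure: 22 × 5 = 110. This is correct in itself.
- Abstract: 105 / 5 = 21 per group, if the groups are equal.
- Difference: 110 − 105 = 5 participants, or 1 per group. That is 5/110 = 4.5% of the larger total and 5/105 = 4.8% of the smaller.

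**2. Could dropout link them?**

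No dropout rate is stated. Dropout appears only as a quantity to be summarised.

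- Inflating 105 for an assumed 5% loss: 105 / 0.95 = 110.5, rounded up to 111. For an assumed 10%: 105 / 0.90 = 116.7, rounded up to 117. Neither gives 110.
- In the other direction, 110 × 0.95 = 104.5, which is close to 105. But 105 would then be the number completing, and the abstract gives it as the number to be recruited. An allowance for dropout makes the recruited number the larger of the two; here it is the smaller.

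**3. What the choice does to power**

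The plan's remark that power is below 0.60 cannot be reproduced, because no test, endpoint, alpha, effect size or SD is given with it. The figures below rest on assumptions that are not in the documents: two-sided alpha 0.05, equal arms, complete data, and d as the difference in SDs of whichever variable is compared.

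For an arm-versus-control t-test with n per arm, power = P(|T| > t(0.975; 2n − 2)), where T is noncentral t with 2n − 2 degrees of freedom and noncentrality d × √(n/2). The critical values are 2.021 (n = 21, 40 df) and 2.018 (n = 22, 42 df). At d = 0.5, for example, the noncentrality is 0.5 × √10.5 = 1.620 for n = 21 and 0.5 × √11 = 1.658 for n = 22.

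| d | 21 per arm | 22 per arm |
|---|---|---|
| 0.2 | 0.097 | 0.099 |
| 0.5 | 0.353 | 0.367 |
| 0.7 | 0.600 | 0.621 |
| 0.8 | 0.716 | 0.736 |
| 1.0 | 0.885 | 0.900 |

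The largest gap over all d is 0.021, near d = 0.74. Power reaches 60% at d = 0.700 with 21 per arm and at d = 0.683 with 22. The plan's remark is therefore true of this test with 22 per arm for differences below about 0.68 SD.

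The ANOVAs move by a similar amount. At an assumed f = 0.25 and alpha 0.05, power is 0.441 against 0.460 for four arms, and 0.489 against 0.511 for five arms (21 against 22 per arm).

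**4. Justification against analysis plan**

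| Sample size justification | Analysis plan |
|---|---|
| Multilevel analyses, described as proposed | None. Descriptive statistics, t-tests and ANOVA only |
| Purpose: relate the trajectories of the outcomes | None. Each outcome is analysed separately, from baseline and week 12 |

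No multilevel, mixed or growth model is specified anywhere else in the documents.

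**The case against.** The strongest reply is that nothing of substance turns on this. The plan openly says that it lacked the information for a calculation, that power will be low, and that high power is not its purpose. Feasibility is analysed descriptively and does not depend on power. The step from 21 to 22 per arm is worth about 2 points. All of that stands, and it limits the weight of the point. It does not remove the contradiction: the document still gives two targets, and its justification still cites an analysis that it does not plan.

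Three stronger readings are tempting, and the documents do not support them.

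- **That the power statement is wrong.** A reader might infer this because the remark is tied to no test. It is a qualitative warning, and it holds over a wide range of effects (below about 0.68 SD for a t-test with 22 per arm). Nothing shows it to be false.
- **That a multilevel model was dropped by mistake.** The design is labelled repeated measures and steps are recorded every week, which might suggest a missing longitudinal model. But two visits per participant already make the design repeated measures, and the paired tests and change scores use them. The step data have stated uses in adherence and in feedback to participants. The multilevel wording could equally be left over from other text.
- **That a trajectory analysis was promised.** The trajectory phrase states a purpose of the pilot. Only multilevel analyses are named as a method.

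**Conclusion.** The point holds as an inconsistency in the stated sample size and its justification. One of the two totals is wrong as written, and the documents do not show which. The gap is 5 participants, or 1 per arm with five equal arms. Its effect on power is at most about 2 percentage points for an arm-versus-control t-test, assuming two-sided alpha 0.05, equal arms and complete data. Separately, the justification rests on multilevel analyses that are not planned, and it states a purpose that no planned analysis addresses. This is not a failed power calculation: the plan makes no calculation and calls itself a low-power pilot. The conflict in totals and the missing model can both be read directly from the text and need no assumption. Only the power figures do.

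**What to change.** 1. The investigator confirms one total and one per-group number and states them in both the Sample paragraph of Section 1 and the Sample size justification of Section 7.
2. The justification is made to match the analysis plan by one of two routes, which the documents do not settle:
   - If no multilevel model is intended, delete the reference to multilevel analyses and the clause on relationships between trajectories. What remains is that prior information was insufficient for a calculation and that the pilot explores feasibility without aiming at high power.
   - If a multilevel model is intended, add it to the Analysis plan with its outcomes and time points, and say how it relates the trajectories.

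The total and the first route cost only wording in two places. The second route adds some analysis of data already being collected. Neither needs new data.
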